3.3.3 Exclusion criteria

Any of the following is regarded as a criterion for exclusion from the study:

1. History of hypersensitivity or adverse reaction to dicalcium phosphate and lactose excipients.
2. Use of a prescription medication for acute or chronic medical conditions within 4 weeks prior to Day 1 of Study Period 1 through completion of Study Period 2;
3. Use of aspirin or any other drug known to increase the propensity for bleeding within 7 days prior to Day 1 of Study Period 1 through completion of Study Period 2 ;
4. Use of NSAIDs (including ibuprofen) within 3 days prior to Day 1 of Study Period 1 through completion of Study Period 2 ;
5. Use of over-the counter preparations including herbal remedies such as *Cordyceps sinensis*, dan shen, feverfew, *Ganoderma lucidum*, ephedra, echinacea, St. John's Wort, and garlic, [aged extract taken on an ongoing basis], ginseng, ginkgo, and vitamin preparations within 7 days prior to Day 1 of Study Period 1 through completion of Study Period 2;
6. History or presence of neurological, haematological, psychiatric, gastrointestinal, hepatic, or renal disease, or other condition known to interfere with the absorption, distribution, metabolism or excretion of drugs;
7. History of post-surgical bleeding or excessive bleeding after dental extraction;
8. History of any first degree atrioventricular block (PR interval >0.2 sec), second or third degree heart block;
9. Screening Period (visit 1) or Day -1 of Study Period 1 ECG with any clinically significant abnormalities or QTc > 480ms;

10. Any previous recent episodes of unexplained syncope;
11. History of vascular abnormalities including aneurysms; a personal history of severe haemorrhage, hematemesis, melena, haemoptysis, severe epistaxis, or intracranial haemorrhage; rectal bleeding within 3 months prior to Screening Period (visit 1);
12. History suggestive of peptic ulcer disease or bleeding diatheses;
13. History of anxiety disorder;
14. Platelet count $<150,000/\text{mm}^3$ at screening;
15. History of alcohol or substance abuse within the past year;
16. Surgery or significant trauma within 3 months prior to Day 1 of Study Period 1;
17. Positive test results for HIV, (human immunodeficiency virus) HBsAg, (hepatitis B surface antigen) or hepatitis C antibody (anti-HCV);
18. Positive urine drug screen;
19. Receipt of an investigational drug or participation in another clinical study within 60 days prior to Day 1 of Study Period 1;
20. Previous participation in an AZD6140 study;
21. Blood donation within 90 days prior to Day 1 of Study Period 1;
22. Clinical judgment, by the investigator, that the volunteer should not participate in the study;
23. A suspected/manifested infection according to WHO risk categories 2, 3 and 4 (Refer to Appendix C);
24. Involvement in the planning and conduct of the study (applies to both AstraZeneca staff or staff at the investigational site).

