The duration of healthy volunteer participation will be approximately 53 days, including:

- **Screening period (visit 1):** within 28 days before Study Period 1, Day 1.
- **Study Period 1 (visit 2):** will consist of admission to the clinical research centre on Day -1, administration of study medication according to randomisation schedule at Day 1, and continued inpatient stay until after the 72 hour post-dose blood collection is performed and all safety assessments are complete.
- **Washout Period:** at least 7 days between discharge from Study Period 1 and dosing of Study Period 2.
- **Study Period 2 (visit 3):** will consist of admission to the clinical research centre on Day -1, administration of study medication according to randomisation schedule at Day 1, and continued inpatient stay until after the 72 hour post-dose blood collection is performed and all safety assessments are complete.
- **Follow-up visit (visit 4):** within 3-5 days of the last inpatient day of Study Period 2.

Variables

- Pharmacokinetic

Treatment A (Oral administration): Blood samples for the pharmacokinetic assessment of AZD6140 and its metabolite AR-C124910XX will be obtained starting on Day 1 of Study Period 1 and Study Period 2 at the following time points:

- Pre-dose, 15min, 30min, 1, 1.5, 2, 2.5, 3, 4, 5, 6, 8, 10, 12, 16, 20, 24, 36, 48, and 72 hours post-dose.

Treatment B (Intravenous administration): Blood samples for the pharmacokinetic assessment of AZD6140 and its metabolite AR-C124910XX will be obtained starting on Day 1 of Study Period 1 and Study Period 2 at the following time points:

- Pre-dose, 15min, 30min, 40min, 50min, 1, 1.25, 1.5, 1.75, 2, 2.5, 3, 4, 5, 6, 8, 10, 12, 16, 20, 24, 36, 48, and 72 hours post dose.

Pharmacokinetics will be assessed by: absolute bioavailability (F), single dose C_{max} , t_{max} , AUMC, $AUC_{(0-t)}$, AUC, and $t_{1/2}$ of AZD6140 and AR-C124910XX, metabolite to parent C_{max} and AUC ratios, CL (IV only), CL/F (oral), V_z and V_{ss} (IV only), MAT (oral), and MRT of AZD6140 only.

- **Pharmacodynamic**

Not applicable.

- **Safety**

Safety and tolerability will be assessed by the incidence and severity of adverse events, vital signs, clinical laboratory parameters, physical examination, and electrocardiograms.

- **Genetics**

Genetic analysis of the genes that are involved in the absorption and disposition, and the response to AZD6140 including adverse effects may be performed.

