1. INTRODUCTION

1.1 Background

Adenosine diphosphate (ADP) is an important mediator of platelet activation and aggregation through its binding to at least 2 distinct subtypes of purinoceptor, designated P2Y₁ and P2Y₁₂, found on platelets. Two ADP receptor antagonists, thienopyridine prodrugs, PLAVIX™ (clopidogrel) and TICLID™ (ticlopidine) have shown clear benefits for the reduction of clinical thrombotic events in patients with atherosclerosis due to their ability to block the P2Y₁₂ receptor. However, this blockade is irreversible and usually incomplete. Therefore, the search continues for agents that can further improve the clinical outcomes of these patients through improved efficacy and/or safety.

AZD6140 is a potent, reversible, selective P2Y₁₂-receptor antagonist (antiplatelet agent) being developed to reduce thromboembolic events in patients with atherosclerosis. It is orally active and does not require metabolic activation, different from clopidogrel, for which only the metabolites are active. Unlike clopidogrel and ticlopidine, which incompletely block the P2Y₁₂-receptor response in humans, pre-clinical studies indicate that AZD6140 can produce reversible and complete inhibition of ADP-induced platelet aggregation *ex vivo* following oral dosing. Additionally, AZD6140 has shown greater and more consistent inhibition of platelet aggregation compared to clopidogrel in both healthy volunteers and patients. It has also demonstrated a faster onset and offset of antiplatelet effect. These properties suggest that AZD6140 may be able to reduce the occurrence of thrombotic events compared to clopidogrel with an acceptable safety profile.

AZD6140 binds to plasma proteins (>99.7%), and is extensively metabolised by CYP3A4/5, with little parent drug excreted unchanged in the urine. AZD6140 has a number of drug–drug interactions of clinical relevance since it is a substrate, inhibitor, and activator of CYP3A4 /5 and a substrate and inhibitor of the P-glycoprotein transporter. Following an oral dose of ¹⁴C-labelled AZD6140 in humans, approximately 27% was excreted in the urine and 57.8% in the faeces. The elimination half-life (t_{1/2}) of the parent compound is approximately 11 hours after single dose administration.

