3.4.4 Concomitant medication

All volunteers should refrain from taking any of the following medications:

- Prescribed medication from 4 weeks prior to the 1st dose of study drug until completion of the assessments and procedures scheduled during the follow-up visit (visit 4) including particular attention to those that are known to inhibit or induce CYP3A isoenzymes.
- Over the counter (OTC) preparations that include herbal remedies and vitamin preparations from 7 days prior to the 1st dose of study drug and through completion of the assessments and procedures scheduled during the follow-up visit (visit 4) including particular attention to those that are known to inhibit or induce CYP3A isoenzymes.
- Aspirin or any other drug known to increase the propensity for bleeding are specifically prohibited within 7 days prior to Day 1 of Study Period 1 and through completion of the assessments and procedures scheduled during the follow-up visit (visit 4).
- NSAIDS (including ibuprofen) within 3 days prior to Day 1 of Study Period 1 and through completion of the assessments and procedures scheduled during the follow-up visit (visit 4).

Any medication, which is considered necessary for the volunteer's safety and well-being, may be given at the discretion of the investigator(s). The administration of all medication (including investigational products) must be recorded in the appropriate sections of the paper case report form (pCRF).

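### The same CYP3A caution carries a 4-week window for prescription drugs and a 7-day window for OTC/herbal products, with no reason given; the possible effect on F is small at trial level but cheap to remove

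*Protocol*

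**What the plan says.** **Prescription drugs, 4 weeks.** Exclusion 2 (section 3.3.3) bars "Use of a prescription medication for acute or chronic medical conditions within 4 weeks prior to Day 1 of Study Period 1". Section 3.4.4 repeats it: "Prescribed medication from 4 weeks prior to the 1st dose of study drug until completion of the assessments and procedures" of the follow-up visit.

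**OTC and herbal products, 7 days.** Exclusion 5 lists herbal products, ending "St. John's Wort, and garlic, [aged extract taken on an ongoing basis], ginseng, ginkgo, and vitamin preparations within 7 days prior to Day 1" (that is, before the first dosing day). Restriction 5 (section 3.3.4) has the same list and the same 7 days. Section 3.4.4 has "Over the counter (OTC) preparations that include herbal remedies and vitamin preparations from 7 days prior to the 1st dose of study drug", without naming products.

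**One caution for both.** In section 3.4.4 the prescription bullet and the OTC bullet each end with the phrase "including particular attention to those that are known to inhibit or induce CYP3A isoenzymes". The protocol gives no reason for the different lengths.

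**Why CYP3A matters here.** Section 1.1 says that AZD6140 "is extensively metabolised by CYP3A4/5, with little parent drug excreted unchanged in the urine". The primary endpoint F (section 6.4.4.1) is the within-volunteer difference in log dose-normalised AUC, oral minus IV. The synopsis separates the periods by "at least 7 days between discharge from Study Period 1 and dosing of Study Period 2".

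**The concern.** A crossover removes a volunteer's CYP3A activity from the oral/IV contrast only if that activity is the same in both periods. By its own caution, the protocol accepts that OTC and herbal products may include CYP3A inducers. It then lets such a product be taken until 8 days before Period 1, whereas a prescription product under the same caution must have stopped 4 weeks before. How fast induction wears off does not depend on whether a product needs a prescription.

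If some induction remains in Period 1 and has largely gone by Period 2, the two AUCs of that volunteer are measured at different clearances. With oral first, oral AUC is lowered and F is too low. With IV first, IV AUC is lowered, so F tends to be too high and CL is too high.

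No mandatory rule catches this. The pharmacokinetics analysis set (section 6.4.3.1) removes volunteers with deviations that interfere with absorption, distribution, metabolism or excretion, and permitted use is not a deviation. Exclusion 6 concerns diseases and conditions, not products.

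**Working it through.** The protocol states no figure to reproduce, so this is a sensitivity calculation.

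**Inputs from the protocol**
- Last permitted herbal use: 8 days before Period 1 dosing, just outside the 7-day window.
- Dose-to-dose gap: inpatient stay to 72 hours (Day 4), plus at least 7 days to the next dose, so 3 + 7 = 10 days at minimum.
- Sequences AB (oral first) and BA (IV first); 10 evaluable volunteers.

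**Assumptions not in the documents**
- Induction wears off with half-life h of 1 to 6 days.
- At full induction, oral CL/F rises by a factor Ro of 1.5 to 2.5 and IV CL by a factor Ri of 1.2 to 1.5. Ro is larger because oral AUC is affected through first pass as well as clearance. Low is paired with low and high with high.

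**Formulas**
- Residual induction: r1 = 2^(−8/h) in Period 1, r2 = 2^(−18/h) in Period 2.
- AUC factor: 1/(1 + (R − 1)r), with R = Ro for oral and Ri for IV.
- Observed/true F: AB = (1 + (Ri − 1)r2)/(1 + (Ro − 1)r1); BA = (1 + (Ri − 1)r1)/(1 + (Ro − 1)r2).

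**Results for one affected volunteer** (low folds, then high folds)

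| h (days) | r1 | r2 | AB | BA |
|---|---|---|---|---|
| 1 | 0.4% | 0.0% | 0.998, 0.994 | 1.001, 1.002 |
| 2 | 6.3% | 0.2% | 0.970, 0.915 | 1.012, 1.028 |
| 3 | 15.7% | 1.6% | 0.930, 0.815 | 1.024, 1.054 |
| 4 | 25.0% | 4.4% | 0.897, 0.743 | 1.027, 1.055 |
| 6 | 39.7% | 12.5% | 0.855, 0.666 | 1.016, 1.009 |

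Example, h = 6 with high folds: AB = (1 + 0.5 × 0.125)/(1 + 1.5 × 0.397) = 1.0625/1.595 = 0.666. BA = (1 + 0.5 × 0.397)/(1 + 1.5 × 0.125) = 1.198/1.1875 = 1.009.

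**IV clearance in Period 1** is too high by (Ri − 1)r1: from 0.2 × 0.004 = 0.1% to 0.5 × 0.397 = 20%.

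**Trial level.** With five volunteers per sequence, each carries weight 1/10 on the log scale. One affected AB volunteer shifts geometric-mean F by at most 0.666^0.1 = 0.960. One affected BA volunteer shifts it by at most 1.055^0.1 = 1.005. One in each sequence gives, at worst, (0.666 × 1.009)^0.1 = 0.961, so balanced sequences do not cancel the error.

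**Sensitivity to the pairing.** At h = 6, equal folds of 1.5 give BA = 1.198/1.0625 = 1.13. Ro = 2.5 with Ri = 1.2 gives AB = 1.025/1.595 = 0.64 and BA = 1.079/1.1875 = 0.91. One volunteer in 10 still moves the mean by about 4% at most (0.643^0.1 = 0.957).

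**Comparison: last use 28 days before Day 1.** r1 falls to 0.0% to 3.9%. AB is 0.95 to 1.00 and BA is about 1.00.

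**The case against.** **The size rests on outside figures.** The documents do not say that St. John's Wort induces CYP3A, or how strongly or how long any herbal product does so. At a half-life of 1 day the error is below 1%. This stands: a reader might infer that 7 days is shown to be too short, and the documents do not show it.

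**There is no contradiction in the windows.** The 7 days is the same in all three places, and the protocol sets windows by product class (NSAIDs have 3 days). A reader might infer that the 4 weeks is a washout designed for CYP3A inducers. It is not: it covers all prescription medication. What remains is that one stated caution has two lengths without explanation.

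**Safeguards exist.** Exclusion 22 allows exclusion on the investigator's judgment, section 3.4.4 asks for particular attention, and the medication history (section 4.4.4.6) records OTC and herbal products taken in the 2 weeks before Day -1. Use ending 8 days before dosing could therefore be seen. This stands in part: none of these obliges anyone to act on what is recorded.

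**The error is not symmetric.** A reader might apply one doubling to both routes and infer IV-first errors of (1 + 0.157)/(1 + 0.016) = 1.14 at h = 3 and (1 + 0.397)/(1 + 0.125) = 1.24 at h = 6. The documents give no such fold. Where the oral effect is the larger, induction left in Period 2 also lowers oral AUC and offsets most of the rise in F.

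**It needs an affected volunteer.** Someone among about 12 healthy volunteers must have used such a product until just outside the window. The documents give no basis for that probability.

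**Conclusion.** The point holds as an unexplained difference between two windows that carry the same CYP3A caution, in a trial whose only primary endpoint depends on stable clearance between periods. On the assumptions listed, with low and high folds paired, an affected volunteer's F is under 1% to about 33% too low if oral comes first and 0 to about 6% too high if IV comes first. The IV-first ceiling depends on the oral effect exceeding the IV effect.

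One affected volunteer in 10 shifts geometric-mean F by at most about 4%. With fast offset the shift is negligible. The documents do not support a claim that the trial's estimate of F would be seriously wrong. The case for change is that a possible source of error, in a comparison with about 10 pairs, can be removed at very little cost.

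**What to change.** Reconcile exclusion 5, restriction 5 and the OTC bullet of section 3.4.4 with the prescription window. Either place OTC and herbal products known to induce CYP3A under the 4-week window that the protocol already uses, or state why 7 days is enough for them. Leave the other OTC and herbal items at 7 days. If the longer window is adopted, the 2-week look-back for medication history in section 4.4.4.6 would need to cover it for these products.

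The cost is one line in each of three places, plus the look-back. A few recent users among about 12 volunteers would be delayed or excluded.

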3.3.4 Restrictions

Volunteers have the following restrictions:

1. Refrain from consumption of alcoholic beverages from 7 days prior to Day 1 of Study Period 1 and through the completion of the follow-up visit (visit 4).
2. Refrain from the consumption of caffeine-containing products from 48 hours prior to Day 1 of Visit 2 through in-patient discharge on Day 4 and from

48 hours prior to returning to Day –1 of Visit 3 through in-patient discharge on Day 4.

3. Refrain from consumption of Seville oranges and grapefruit-containing products from 7 days prior to Day 1 of Study Period 1 through the completion of the follow-up visit (visit 4);
4. Refrain from strenuous exercise from 48 hours prior to Day 1 of Study Period 1 through the completion of the follow-up visit (visit 4). Volunteer will have reduced physical activity for 72 hours in the unit under constant monitoring;
5. Refrain from the use of over-the-counter preparations including herbal remedies such as *Cordyceps sinensis*, dan shen, feverfew, *Ganoderma lucidum*, ephedra, echinacea, St. John's Wort, and garlic, [aged extract taken on an ongoing basis], ginseng, ginkgo, and vitamin preparations from 7 days prior to Day 1 of Study Period 1 through completion of the follow-up visit (visit 4);
6. Refrain from the use of aspirin or any other drug known to increase the propensity for bleeding from 7 days prior to Day 1 of Study Period 1 through completion of the follow-up visit (visit 4);
7. Refrain from the use of NSAIDs (including ibuprofen) from 3 days prior to Day 1 of Study Period 1 through completion of the follow-up visit (visit 4);
8. Refrain from scheduling or having surgery, including dental surgery, at anytime following the Screening Period (visit 1), and through completion of the follow-up visit (visit 4);
9. Refrain from the use of tobacco or other nicotine-containing products from Screening Period (visit 1) and throughout the follow-up visit (visit 4).

3.3.5 Discontinuation of volunteers from treatment or assessment

3.3.5.1 Criteria for discontinuation

Volunteers may be discontinued from study treatment and assessments at any time. Specific reasons for discontinuing a volunteer from this study are:

1. Voluntary discontinuation by the volunteer, who is at any time free to discontinue his/her participation in the study without prejudice to further treatment.
2. Safety reasons as judged by the investigator and/or AstraZeneca.
3. Severe non-compliance to protocol as judged by the investigator and/or AstraZeneca.

4. Incorrect enrolment i.e., the volunteer does not meet the required inclusion/exclusion criteria for the study.
5. Volunteer lost to follow-up.

Specific reasons for discontinuing a volunteer from the genetic research when genetics is a secondary objective of the study are:

- Withdrawal of consent for genetic research. A volunteer may withdraw from this genetic research at any time, independent of any decision concerning participation in other aspects of the main study described in this protocol. Voluntary discontinuation by the volunteer will not prejudice further treatment.

3.3.5.2 Procedures for discontinuation

Volunteers who discontinue should always be asked about the reason(s) for their discontinuation and the presence of any adverse events. If possible, they should be seen and assessed by an investigator(s). Adverse events should be followed up.

If a volunteer is being withdrawn due to a suspected infection in WHO risk categories 2, 3, and 4 as defined in Appendix C, no biological samples from this volunteer are allowed to be sent to the laboratory. Samples will be destroyed according to normal routines at the study site.

If a volunteer is withdrawn or drops out, he/she will be replaced at the discretion of the sponsor.

3.3.5.3 Procedures for handling incorrect enrolled volunteers

Volunteers not meeting the inclusion/exclusion criteria for this study must, under no circumstances, not be enrolled into this study; there can be no exceptions to this rule. Where volunteers not meeting the study criteria are enrolled in error, incorrectly randomised, or where volunteers subsequently fail to meet the criteria for the study, the volunteer should return for the procedures and assessments scheduled for the follow-up visit if study drug has been administered.

3.3.5.4 Procedures for discontinuation from genetic aspects of the study

Volunteers who discontinue from the study should always be asked specifically whether they are withdrawing or continuing their consent for this linked genetic research. It must be established whether the volunteer:

- Agrees to the genetic sample and any DNA extracted from the sample being kept for genetic analyses in the future.
- Withdraws consent for the sample to be kept for genetic analysis in the future and wishes the sample to be destroyed. Destruction of the sample (or the DNA extracted from the sample) will only be possible so long as the particular sample

is traceable. In the event that genetic research has already been performed, AstraZeneca will retain the results and associated data for regulatory reasons but these will not be used in any subsequent analyses.

The principal investigator is responsible for providing written notification to AstraZeneca of any volunteer who has withdrawn consent for the use of the sample taken for genetic research. AstraZeneca will provide written confirmation to the investigator of the actions taken with the sample, which must be filed in the investigator study file.

3.4 Treatment(s)

3.4.1 Investigational product(s)

3.4.1.1 Identity of investigational product

Table 3 Identity of investigational product

Investigational product	Dosage form and strength	Manufacturer	Formulation number	Batch number
AZD6140	Yellow, oval, biconvex, film coated 90 mg tablets	AstraZeneca	FDN 334	*
AZD6140	15 mg intravenous infusion	AstraZeneca	FDN 308	*

* The batch number will be recorded in the study master file and identified in the Clinical Study Report.

3.4.1.2 Labelling

AZD6140 tablets will be packaged as open-label, bulk supply, 60 tablets per bottle and labelled with a single panel.

AZD6140 IV solution will be packaged, open-label, in 50 mL vials, labelled with a single panel. Each volunteer will require a total of 4 vials for the 150 mL infusion. One of the vials will be used for priming the infusion lines and pump.

The supplies will be labelled including the following information in accordance with Good Manufacturing Practice (GMP) and local regulatory requirements:

- Name of sponsor and address
- Pharmaceutical dosage form
- Route of administration
- Number of dosage units
- Study code

- USA caution statement
- Keep out of the reach of children

The investigational products will be supplied as bulk supply. Study site dispensary staff will dispense the investigational product. Individual dosing containers will be labelled with the study number, volunteer number and study day.

